## APPENDIX 2 SAS CODE FOR STATISTICAL ANALYSES

This section will be completed after examining the existing data and prior to the final signoff of this SAP.

Test	Template SAS Code for Modeling (SAS Version 9.4)
Linear Repeated Measures Analysis of Covariance for the primary endpoint	<pre> PROC MIXED METHOD=REML;   CLASS SUBJECT TRT VISIT BASEHSSTAGE;   MODEL Y = BASE TRT VISIT TRT VISIT/ DDFM=KR SOLUTION   OUTP=OUT;   REPEATED VISIT / TYPE = UN SUBJECT = SUBJECT;   LSMEANS TRT VISIT / PDIFF CL ALPHA=0.1;   ODS OUTPUT LSMEANS=MEANS;   ODS OUTPUT DIFFS=DIFF;   RUN; </pre> 
Where TRT is treatment, VISIT is the study visit number, BASEHSSTAGE is the baseline Hurley Stage, and BASE is the baseline of outcome variable.

General Estimating Equation Repeated Measures with Generalized Logit Transformation	<pre> PROC GENMOD;   CLASS SUBJECT TRT VISIT BASEHSSTAGE;   MODEL Y= BASE TRT VISIT TRT*VISIT / LINK=LOGIT DIST=NEGBIN;   REPEATED SUBJECT=SUBJECT / TYPE=UN;   LSMEANS TRT VISIT / DIFF CL ALPHA=0.1;   ODS OUTPUT LSMEANDIFFS = LSDIFS ESTIMATES=EST   LSMEANS=LSMEANS PARAMETERESTIMATES=PE; </pre> 
Where TRT is treatment, VISIT is the study visit number, BASEHSSTAGE is the baseline Hurley Stage, and BASE is the baseline of outcome variable.

General Estimating Equation Repeated Measures for secondary and exploratory endpoints	<pre> PROC GENMOD;   CLASS SUBJECT TRT VISIT;   MODEL Y = TRT VISIT TRT*VISIT/ DIST=BIN LINK=LOGIT;   REPEATED SUBJECT = SUBJECT /TYPE=UN;   RUN; </pre> 
Where TRT is treatment and VISIT is the study visit number.

Test	Template SAS Code for Modeling (SAS Version 9.4)
Impute Intermittent Missing using the Monte Carlo Markov Chain (MCMC) approach	<pre> PROC MI DATA=data_in SEED=2330710 NIMPUTE=100 OUT=LESION_MONO;   BY BASEHSSTAGE TRT; /*Assuming different treatment, baseline Hurley Stage has different distribution*/   MCMC CHAIN=MULTIPLE IMPUTE=MONOTONE; /*Only impute intermittent missing values*/   VAR AGE BASE AN1 – AN5; /*Impute AN count from Week 4 to Week 16, with age and baseline as covariates*/   RUN; </pre>
Multiple Imputation with FCS Method	<pre> PROC MI MIN=0 ROUND=1;   CLASS BASEHSSTAGE TRT SEX;   FCS REGPMM(AN2 = AN1 AGE SEX TRT BASE BASEHSSTAGE );   FCS REGPMM(AN3 = AN1 AN2 AGE SEX TRT BASE BASEHSSTAGE );   FCS REGPMM(AN4 = AN1-AN3 AGE SEX TRT BASE BASEHSSTAGE );   FCS REGPMM(AN5 = AN1 AN4 AGE SEX TRT BASE BASEHSSTAGE );   VAR AN1 – AN5 AGE SEX TRT BASE BASEHSSTAGE;   RUN; </pre>
Combine Parameter Estimates for LSmeans	<pre> PROC MIANALYZE DATA=OUTREG;   BY VISIT;   MODELEFFECTS TRT; /* TRT IS THE VARIABLE FOR LS TREATMENT DIFFERENCES */   STDERR TRTERR; /* TRTERR IS THE STANDARD ERROR FOR TREATMENT DIFFERENCES */   RUN; </pre>
Cochran-Mantel-Haenszel ANOVA statistics (row means score)	<pre> PROC FREQ;   TABLES BASEHSSTAGE *TRT*X/CMH2 ALPHA=0.1 SCORE=RANK;   RUN; </pre> 
Where BASEHSSTAGE is randomized Hurley Stage, TRT is treatment, and X is the outcome variable.

Ordinal Logistic Regression using PROC LOGISTIC	<pre> PROC LOGISTIC;   CLASS TRT BASE;   MODEL Y = TRT BASE;   RUN; </pre> 
Where Y is the ordinal outcome variable, TRT is treatment, BASE the baseline of outcome variable.

Exact unconditional CI	<pre> PROC FREQ;   TABLES TRT*X;   EXACT OR;   RUN; </pre>

Test	Template SAS Code for Modeling (SAS Version 9.4)
	Where TRT is treatment, and X is the outcome variable.
Obtaining generalized risk difference	<pre>PROC FREQ;   TABLES TRT*X / ALL LIST MISSING;   TEST SMDCR; RUN;</pre> 
Where TRT is treatment, and X is the outcome variable.

Weighted Kappa and confidence interval	<pre>PROC FREQ;   WEIGHT COUNT;   TABLES BASEHSSTAGE*TRT*X/AGREE ALPHA=0.1; RUN;</pre> 
Where BASEHSSTAGE is Hurley Stage at baseline, TRT is treatment, and X is the outcome variable.

Test of treatment difference for agreement	<pre>PROC FREQ;   TABLES BASEHSSTAGE*TRT*X/CMH2; RUN;</pre> 
Where BASEHSSTAGE is Hurley Stage at baseline, TRT is treatment, and X is the Cicchetti-Allison weight of outcome variable. Cicchetti-Allison weight = 1- abs(CHG)/(k-1), where k = number of categories of the outcome variable.

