#### 9.4.5 ANALYSIS OF THE PRIMARY EFFICACY ENDPOINT

The primary efficacy endpoint is the change from Baseline in AN count at Week 16.

The primary estimand, comprising four components, is defined as follows:

- a) The target population consists of subjects with hidradenitis suppurativa who are eligible to be included in the clinical trial based on the inclusion/exclusion criteria in the protocol. The ITT analysis set will include all randomized subjects. For the analysis, treatment will be assigned based upon the treatment arm to which subjects are randomized regardless of which treatment they receive.
- b) The primary variable is the change from baseline in AN count of an individual subject at Week 16.
- c) To handle intercurrent events such as use of rescue medications, the hypothetical strategy for estimand will be used. Data collected following receipt of rescue medication (if any) will be considered missing in the analysis.
- d) The population-level summary measures will be the population mean differences in the primary variable between each dose of imsidolimab and placebo at Week 16.

A general linear mixed effects model for repeated measures (MMRM) analysis will be used to estimate the least squares means (LSM) and associated standard errors for the change from Baseline in AN count to Week 16. The model will include change from Baseline in AN count at Week 16 as the dependent variable, fixed effects for treatment arm, categorical time point, and the treatment by time point interaction, and the Baseline AN count and stratification factor (ie, Hurley Stage at baseline (Stage II or III)) as covariates. An unstructured covariance structure will be used. The difference between LSMs (imsidolimab – placebo) at Week 16 will be presented along with the associated 90% CI and p-value. The ITT analysis set will be used for the primary efficacy analysis.

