#### 9.4.6.1 CATEGORICAL ENDPOINTS

Frequency and percentages for each response Yes/No for categorical endpoints will be presented separately by visit for each treatment arm. Subjects with missing scores at a given visit will be considered to have not met the criteria of interest (ie, nonresponse). Estimates of the difference between treatments (imsidolimab – placebo) will be presented along with exact 90% CIs. Treatment arms will be compared using Cochran–Mantel–Haenszel chi-squared test, adjusted for stratification factor (Hurley Stage at baseline (Stage II or III)).

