### 7.5 Efficacy Analyses

The ITT Analysis Set will be used as the primary analysis set for all efficacy analyses in the placebo-controlled period. The Extension Analysis Set will be used as the main analysis set for all efficacy analyses in the extension period.

Per protocol analyses will be performed on the primary as well as the following secondary endpoints:

- Percent change from baseline in AN count at each visit
- Proportion of subjects achieving HiSCR50 at each visit
- Change from baseline in HS Pain NRS at each visit
- Percent change from baseline in HS Pain NRS at each visit

All statistical tests will be performed at the 10% level of significance unless otherwise stated. All confidence intervals will be reported as 2-sided 90% confidence intervals unless otherwise stated. Descriptive statistics will be provided for the continuous variables as number of subjects, mean, standard deviation, standard error of the mean, first and third quartiles, minimum, and maximum. Descriptive summaries of continuous variables will be shown for baseline, change from baseline to endpoint, and percent change from baseline to endpoint. All data will be listed in data listings.

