#### 7.5.1 Primary Efficacy Estimand

The primary estimand, comprising five components, is as follows:

- a) The target population is subjects in the United States and Europe diagnosed for at least 6 months with HS, having lesions at Hurley Stage II or III.
- b) The primary variable is the change from baseline in AN count of an individual subject at Week 16.
- c) To handle intercurrent events such as use of rescue medications, a hypothetical strategy for estimand (**ICH E9, 2019**) will be used such that data collected following receipt of rescue medication (if any) will be considered missing in the analysis. Missing values will be imputed as described in **Section 7.5.4**. The hypothetical scenario envisaged under this estimand is what value the primary variable would have taken if the subject had not taken rescue treatment.

- d) The population-level summary measure for the primary endpoint is mean change from baseline in AN count at Week 16. The estimator for between-group comparison of the primary endpoint will be the difference in the primary endpoint between imidolimab and placebo at Week 16.
- e) The treatment conditions of interest, two imidolimab treatment regimens and one placebo regimen:
  1. Imsidolimab 400 mg injection on Day 1, followed by 200 mg on Days 29, 57, and 85;
  2. Imsidolimab 200 mg injection on Day 1, followed by 100 mg on Day 29, 57, and 85;
  3. Placebo on Days 1, 29, 57, and 85

A linear mixed model will be used for the repeated measures (MMRM) with treatment, visit, treatment by visit interaction, and Hurley Stage at baseline as a categorical covariate and baseline AN count as a continuous covariate. An unstructured correlation (UN) matrix will be used to model correlation within a patient; if convergence is an issue, a Toeplitz structure may be considered. If convergence issue persists, elimination of post-baseline visits other than Week 16 may be considered. Subjects with missing data at Week 16 due to early discontinuation will be included in the model.

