## 7.5.2 Secondary Efficacy Analyses

### 7.5.2.1 Percent change from baseline in AN count at Week 16

This secondary endpoint will be analyzed using a similar MMRM model as for the primary endpoint. The percent change from baseline in AN count at Week 16 will be the response variable.

### 7.5.2.2 Proportion of subjects achieving HiSCR50 at Week 16

The frequency and percentage of subjects with HiSCR50 will be summarized at Week 16. The unadjusted risk difference and 90% exact unconditional confidence intervals will be reported between the imidolimab and placebo groups for all subjects and Hurley Stage at randomization (Stage II or III). The common risk difference will also be tested using a generalized Cochran-Mantel-Haenszel test (ANOVA for row means), adjusting for Hurley Stage at randomization.

A sensitivity analysis will be conducted for this endpoint on the ITT Analysis Set where subjects received rescue medications between Week 4 and Week 16 will be considered as failure to achieve HiSCR50 at Week 16.

An additional exploratory analysis will be performed for the proportion of subjects achieving HiSCR50 by visit. A repeated-measures generalized estimating equations (GEE) with the logit link will be used. The model will include treatment, visit, treatment by visit interaction, race, gender, Fitzpatrick skin type, Hurley Stage at baseline, and baseline inflammatory lesion count as covariates. Data from protocol specified visits up to Week 16 will be included in the analysis. An unstructured correlation matrix will be used to model correlation within a patient; if convergence is an issue, a Toeplitz structure may be considered. An odds ratio resulting from this model along with 90% CI will be reported.

### 7.5.2.3 Change from Baseline in Average HS pain NRS at Week 16

Change from baseline in Average HS pain NRS at Week 16 will be analyzed using a similar MMRM model as for the primary endpoint, but changing baseline AN count to HS pain NRS in the model as the response.

### 7.5.2.4 Percent change from Baseline in Average HS pain NRS at Week 16

Percent change from baseline in Average HS pain NRS at Week 16 will be analyzed similarly to percent change from baseline in AN count at Week 16, as described in **Section 7.5.2.1**.

### 7.5.2.5 Change from Baseline in Worst HS pain NRS at Week 16

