### Additional Exploratory Efficacy Analyses

To estimate the treatment effect while accounting for a subject knowing they are on study drug, the primary endpoint analysis will be repeated comparing the estimated change from Day 1 imsidolimab baseline to Week 16 (for active dose subjects in the placebo-controlled period) to the estimated change from Week 16 imsidolimab baseline to Week 32 (for placebo → imsidolimab subjects). This comparison will be done separately for like doses (arm 1 to arm 3A, and arm 2 to arm 3B.)

To further estimate the treatment effect while accounting for a subject knowing they are on study drug and while also accounting for inter-subject variability, the primary endpoint analysis model as described in **Section 7.5.1**, will be fitted. A binary indicator variable will be added to the model to indicate visits at which the subject knows they are on study drug. The change from imsidolimab baseline between Week 16 and Week 32 for the placebo → imsidolimab group will be compared within treatment regimen. The overall treatment effect at 16 weeks will be estimated with the primary independent group contrast at Week 16 as well as the cross-over contrast between Week 16 and Week 32 for the placebo → imsidolimab group. Furthermore, the effect of 32 weeks of exposure compared to 16 weeks of exposure will be estimated comparing like doses.

The change from baseline and percent change from baseline in the calculated composite total of abscess, inflammatory nodule, and draining fistula count at each visit, and percent change from baseline in the draining fistula count at each visit will be analyzed using a similar MMRM model as described for the primary efficacy analysis in **Section 7.5.1**, but changing baseline AN count to baseline of the outcome variable and adding Hurley Stage at baseline as an additional covariate. Summary statistics and the results of statistical testing at each visit will be provided for each continuous exploratory variable.

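### Two Appendix 2 code templates in SAP V1.0 do not match the analyses the text specifies: the primary model line leaves out Hurley stage, and the exact-interval code requests an odds ratio instead of the 90% risk-difference interval

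*SAP*

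**What the plan says.** **Primary model.** Protocol 9.4.5 includes "the Baseline AN count and stratification factor (ie, Hurley Stage at baseline (Stage II or III)) as covariates". SAP 7.5.1 agrees: "A linear mixed model will be used for the repeated measures (MMRM) with treatment, visit, treatment by visit interaction, and Hurley Stage at baseline" enters as a categorical covariate, with baseline AN count as a continuous one. The primary-endpoint `PROC MIXED` template in SAP Appendix 2 names `BASEHSSTAGE` in its `CLASS` statement and defines it in the legend as baseline Hurley stage. Its model line is "MODEL Y = BASE TRT VISIT TRT VISIT/ DDFM=KR SOLUTION". The legend defines `BASE` separately, as the baseline of the outcome.

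**HiSCR50 interval.** SAP 7.5.2.2 states: "The unadjusted risk difference and 90% exact unconditional confidence intervals will be reported", for all subjects and by Hurley stage. Protocol 9.4.6.1 says that estimates of the treatment difference "will be presented along with exact 90% CIs". SAP 7.5 sets the general rule: "All confidence intervals will be reported as 2-sided 90% confidence intervals unless otherwise stated". The Appendix 2 template titled Exact unconditional CI consists of a `TABLES TRT*X` request and `EXACT OR`. It has no risk-difference request and no alpha setting. The Cochran-Mantel-Haenszel template in the same table does set the level: "TABLES BASEHSSTAGE *TRT*X/CMH2 ALPHA=0.1 SCORE=RANK".

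**Status.** The SAP cover shows V1.0 with a sign-off date of 16-Aug-2022. Appendix 2 still opens by saying that it is to be completed before final signoff. No sentence in the SAP says whether text or template prevails when they differ.

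**The concern.** An analyst who programs from Appendix 2 and one who programs from Section 7 would produce different results for the primary endpoint and for the HiSCR50 interval, and each could cite the signed SAP.

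For the primary endpoint, the stratification factor would be missing from the model. That gives up whatever precision it offers beyond baseline AN count. It also removes a covariate from a model that, according to SAP 7.1.2, relies on data being missing at random. That matters because 10% dropout is planned and data after rescue are set to missing.

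For HiSCR50, the template output differs from the specification in three ways: odds ratio instead of risk difference, conditional instead of unconditional exact method, and 95% instead of 90%. A reader would see a different quantity, and in some data sets a different answer to whether the interval excludes no effect.

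**Working it through.** **1. The plan's own power figure.** Inputs from protocol 9.2 and SAP 3.5: 36 evaluable per arm, difference 4.9, SD 8.2, two-sided alpha 0.10, two-sample t-test.

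- Standard error = 8.2 × √(2/36) = 1.933
- Noncentrality = 4.9 / 1.933 = 2.535, with 70 degrees of freedom and critical value 1.667
- Power = 80.7%

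The stated 80% is reproduced. The calculation uses no covariates, so it stands whether or not Hurley stage is in the model.

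**2. Cost of leaving Hurley stage out.** If Hurley stage explains a share R² of the residual variance beyond baseline AN count, omitting it multiplies the standard error by 1/√(1 − R²). The documents give no R², so the range is an assumption.

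| Assumed R² | SE multiplier |
|---|---|
| 0 | 1.000 |
| 0.05 | 1.026 |
| 0.10 | 1.054 |
| 0.15 | 1.085 |

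**3. What the interval template returns against what the text specifies.** The documents give no expected HiSCR50 rates, so the responder counts are assumptions. The denominator is an assumption too. It is 36 per arm if only subjects with HiSCR50 data count, as in SAP 6.2.3. It is about 40 if missing counts as nonresponse, as in protocol 9.4.6.1. The odds-ratio limits are conditional exact (noncentral hypergeometric). The risk-difference limits invert two one-sided exact tests on the unstandardised difference, maximised over the nuisance rate.

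| Counts | Measure | Estimate | 95% interval | 90% interval |
|---|---|---|---|---|
| 20/36 vs 11/36 | Odds ratio | 2.84 | 0.977 to 8.394 | 1.133 to 7.134 |
| 20/36 vs 11/36 | Risk difference | 0.250 | 0.006 to 0.473 | 0.043 to 0.441 |
| 18/36 vs 11/36 | Odds ratio | 2.27 | 0.783 to 6.695 | 0.909 to 5.699 |
| 18/36 vs 11/36 | Risk difference | 0.194 | -0.050 to 0.422 | -0.013 to 0.390 |
| 20/40 vs 12/40 | Odds ratio | 2.33 | 0.851 to 6.491 | 0.980 to 5.569 |
| 20/40 vs 12/40 | Risk difference | 0.200 | -0.031 to 0.416 | 0.004 to 0.385 |

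The template gives the odds-ratio row at 95%; the text asks for the risk-difference row at 90%.

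- **20/36 vs 11/36:** the template interval includes 1 and the specified interval excludes 0. Correcting the level alone or the measure and method alone would restore agreement.
- **20/40 vs 12/40:** the odds-ratio interval includes 1 even at 90%, while the specified interval just excludes 0. Correcting the level alone is not enough.
- **18/36 vs 11/36:** all four intervals include no effect, so that conclusion is the same and only the reported quantity differs.

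**The case against.** The case for leaving this alone is substantial. The column is labelled as template code, and other entries are skeletal too. The GEE template for secondary endpoints omits most covariates listed in 7.5.2.2, the FCS template omits race, and the ordinal logistic template omits Hurley stage. Naming `BASEHSSTAGE` in `CLASS` and in the legend shows that it was meant to be in the primary model. The text is explicit in both documents. Dry runs on blinded data (SAP 3.4) and a programming quality-control plan (SAP Section 4) may catch both errors. The table shells are in a separate document, so what would finally be printed for HiSCR50 cannot be established here. All of this stands and limits the severity. It does not make the templates right: completed as written, they run a different analysis.

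Some stronger readings are tempting but not supported:

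- **That the primary comparison would be biased or underpowered.** With complete data, omitting a stratification factor is not expected to bias a randomised comparison, and the power figure never used it. No bias cannot be promised under missing data, but the documents do not show that missingness depends on Hurley stage.
- **That SAP 7.5.3 shows the primary model lacks Hurley stage.** For some additional exploratory endpoints it describes the 7.5.1 model "but changing baseline AN count to baseline of the outcome variable and adding Hurley Stage at baseline as an additional covariate". Because 7.5.1 already contains the term, this is redundant wording, not evidence of omission.
- **That the silence of SAP Section 8 is telling.** That section lists departures from the protocol. The protocol and SAP text agree on both analyses, so there was nothing to list.
- **That the HiSCR50 discrepancy is only a confidence-level slip.** The 20/40 against 12/40 case shows otherwise.
- **That the model line also drops the interaction.** An asterisk may have been lost when the PDF was read. That cannot explain a missing variable name: the first `PROC GENMOD` template keeps its asterisk and also leaves `BASEHSSTAGE` out of its model.

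**Conclusion.** The point holds as a conflict between code and text in a signed-off SAP, in two places.

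1. The primary template omits a covariate that both documents require. The precision loss cannot be sized from the documents; it is 0 to 8.5% on the standard error for an assumed R² of 0 to 0.15. The model would also lose a covariate that supports the missing-at-random assumption. The 80% power is unaffected.
2. The exact-interval template differs from the specification in parameter, method and confidence level. Measure and method on the one hand, and level on the other, can each change whether the interval excludes no effect. The illustrations rest on assumed counts and denominators, and on one version of the exact unconditional interval.

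The consequence is modest. HiSCR50 is a secondary endpoint whose testing SAP 3.3 calls exploratory, and the text shows which analysis is meant. The templates should still be corrected, because one of them is the code for the primary endpoint and the SAP gives no rule of precedence.

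**What to change.** - Add `BASEHSSTAGE` to the `MODEL` statement of the primary `PROC MIXED` template.
- Replace the interval code with `TABLES TRT*X / RISKDIFF ALPHA=0.1; EXACT RISKDIFF;`, run for each imsidolimab dose against placebo, overall and within each Hurley stage. Adding `ALPHA=0.1` to the existing code is not enough, because it would still return an odds ratio.
- Replace the opening sentence of Appendix 2 with a statement that the SAP text governs wherever a template differs. This also covers the other abbreviated templates.
- Optionally, delete the redundant Hurley clause in SAP 7.5.3.

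The cost is a few lines of code and one or two sentences. No new data are needed, and the specified analyses do not change.

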### 6.2.2 Primary Efficacy Variable

The primary endpoint for this study is the **change from baseline in abscess and inflammatory nodule (AN) count at Week 16**. The AN count is defined as the sum of the number of abscesses and inflammatory nodules (from all locations) from the CRF. For the change from baseline in AN count, the difference in AN count taken between Week 16 and baseline will be computed for each treatment group and overall. The AN count will be assessed at the visits specified in the Schedule of Activities in **Section 3.6**.

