## 7.5.4 Sensitivity Analyses

A number of sensitivity analyses are planned to evaluate the robustness of the primary and secondary efficacy results.

For the primary efficacy endpoint, the following sensitivity analyses will be performed:

- Analysis of primary efficacy endpoint using the PP Analysis Set.
- Analysis of primary efficacy endpoint using the specified MMRM model but including additional covariates of race, smoking, age, and Fitzpatrick skin type as model convergence allows.
- Multiple imputation with FCS method (described below).
- Tipping point analysis (described below).
- Prior to database lock and unblinding, the assumption of normality in the change from baseline in AN count will be checked by visually inspecting the distribution of the residuals. If the normality assumption is not met, a repeated-measure GEE approach with an appropriate distribution (e.g. logarithm or generalized logit transformation) will be considered. An unstructured correlation matrix will be used in the model if GEE is decided to be used. However, the results from the primary efficacy analysis will be considered the primary efficacy results.

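### The Appendix 2 template for the conditional GEE sensitivity analysis of AN count pairs a negative binomial distribution with a logit link, which suits neither the count nor its change from baseline

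*SAP*

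**What the plan says.** SAP 7.5.4 lists sensitivity analyses for the primary endpoint. In the last of them, "the assumption of normality in the change from baseline in AN count will be checked by visually inspecting the distribution of the residuals", and this is to happen before database lock and unblinding. The text continues: "If the normality assumption is not met, a repeated-measure GEE approach with an appropriate distribution (e.g. logarithm or generalized logit transformation) will be considered". It adds: "An unstructured correlation matrix will be used in the model if GEE is decided to be used". The item closes by keeping the results of the primary efficacy analysis as the primary results.

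SAP Appendix 2 has one template that matches, titled "General Estimating Equation Repeated Measures with Generalized Logit Transformation". It is a PROC GENMOD step with an unstructured working correlation and the statement "MODEL Y= BASE TRT VISIT TRT*VISIT / LINK=LOGIT DIST=NEGBIN". The options at issue are "LINK=LOGIT DIST=NEGBIN". Its note defines treatment, visit, baseline Hurley Stage and the baseline of the outcome variable. It does not define Y. Baseline Hurley Stage is in the CLASS statement but not in MODEL. The GEE for binary endpoints is a separate template with a binomial distribution and a logit link, so the negative binomial block is not the HiSCR50 model.

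On the scale of the outcome, SAP 6.2.2 states: "The AN count is defined as the sum of the number of abscesses and inflammatory nodules". SAP Appendix 1 defines change from baseline as the Week x value minus the baseline value. SAP 3.1 and Protocol 5.1 (inclusion criterion 4) require a count of at least 5 at entry and set no maximum.

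**The concern.** The distribution and the link contradict each other for this outcome. A logit link is made for a mean that is a proportion. A negative binomial distribution is made for an unbounded non-negative count. The template can be read with Y as the AN count or as the change from baseline, and it is invalid on both readings.

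This analysis is the plan's check on the normality assumption of the primary model. That assumption could plausibly fail: counts have a floor at entry and no ceiling, and a subject's count cannot fall by more than its baseline value. If the check were called on, the analysis as coded would give no valid estimate and the team would have to write another specification at that point. Leaving Hurley Stage out of MODEL would also drop the stratification factor that SAP 7.5.1 puts in the primary model.

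**Working it through.** The plan gives no figure for this analysis. Its only design figure is 80% power for a difference of 4.9 lesions, with SD 8.2, 36 per arm and two-sided alpha 0.10 (Protocol 9.2, SAP 3.5). It reproduces: the noncentrality is 4.9 / (8.2 × √(2/36)) = 2.54 on 70 degrees of freedom, and the power is 0.807. The point here does not depend on that power, but step 2 uses the 4.9.

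**1. Range of the fitted mean.** Under a logit link, mean = 1 / (1 + exp(−η)), which lies strictly between 0 and 1 for every η. Baseline is a covariate in this model, so the comparison that matters is with post-baseline counts. A subject at the entry minimum would need a mean fall of more than (5 − 1)/5 = 80% to reach a mean below 1. The model imposes a mean below 1 in every arm, placebo included, and at every visit.

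**2. Size of effect the model can express.** Two means that both lie between 0 and 1 differ by less than 1. Randomisation makes the arms' mean baseline counts equal in expectation, so a 4.9-lesion difference in mean change is also a 4.9-lesion difference in mean Week 16 count. That cannot be represented. Nor can any scenario in Protocol Table 6, where the smallest difference is 2 lesions.

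**3. Y as change from baseline.** Week x minus baseline is negative for any subject whose count falls. A negative binomial variable takes the values 0, 1, 2 and upward. A single improving subject is enough to put the data outside the distribution, whatever the link.

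**4. Numerical illustration.** The documents give no AN distribution, so the data here are simulated and the settings are assumptions: two arms of 36, four visits (288 observations), baseline counts of 5 or more, and dispersion 0.5. The post-baseline mean was 6.68, 85% of counts exceeded 1, and changes ran from −23 to 16 with 77% negative.

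Intercept-only negative binomial with logit link, Y = count:

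| η | Fitted mean | Log-likelihood |
|---|---|---|
| 0 | 0.500 | −2711.2 |
| 2 | 0.881 | −1976.6 |
| 5 | 0.993 | −1841.2 |
| 10 | 0.99995 | −1833.92 |
| 20 | just below 1 | −1833.87 |
| no link constraint, at the sample mean | 6.68 | −836.8 |

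The score is Σ(y − mean)/(mean + 0.5 mean²) × mean × (1 − mean). It is positive at every η because the sample mean exceeds 1. At η = 0 it is 288 × (6.677 − 0.5) / 0.625 × 0.25 = 711.6. It shrinks towards zero as η grows and never reaches it, so there is no finite solution.

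GEE fits with baseline count, treatment, visit and treatment by visit (exchangeable working correlation, Hurley Stage not simulated):

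- Logit link: statsmodels rejects the negative binomial and logit pair as an invalid link, for the count and for the change.
- Log link, Y = count: converges, with fitted means from 2.7 to 58.5.
- Log link, Y = change: fails, because the deviance is undefined for negative values.

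SAS was not available. Whether GENMOD would stop, discard negative values or return a non-converged fit was not tested. None of these outcomes would be a valid estimate.

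**The case against.** The case against giving this much weight is strong, and most of it stands.

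- **It is only a conditional sensitivity analysis.** A GEE is to be considered if normality fails, and the MMRM remains primary either way. This stands. A reader might infer that the primary result is at risk. It is not: no primary estimate, interval or p-value depends on this template.
- **The coded version is not the only route.** A reader might infer that the trial has no usable fallback. SAP 7.5.4 offers its transformations as examples and names the logarithm first, and Protocol 9.4.1 allows nonparametric methods when normality is violated. This stands. Neither alternative has a stated outcome, link or effect measure, however, so the invalid version is the only one written out.
- **The replacement would not be chosen on results by arm.** A reader might infer that it would. SAP 7.5.4 places the normality check before database lock and unblinding, so the documents do not support that inference.
- **Appendix 2 is a template to be completed.** This explains the error but does not cure it. Completion was due before final sign-off, and the SAP is V1.0 with a sign-off date of 16 August 2022.
- **Generalized logit could mean rescaling a bounded outcome to the interval from 0 to 1.** No bounds or rescaling are given, the count has no upper bound, and a negative binomial distribution would not suit a rescaled variable.
- **The error would probably surface when the code is run or quality-checked.** That is likely, and it makes silent bias in a reported result improbable. It does not supply the missing specification.

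**Conclusion.** The template is wrong as written and should be corrected. With Y as the count, fitted means cannot reach 1 and no between-arm difference of 1 lesion or more can be expressed. With Y as the change, the distribution excludes every improving subject. Both statements follow from the definitions of the link and the distribution. The first assumes only that mean AN counts are not below 1 in every arm at every visit, and the second that at least one subject improves. The log-likelihoods and the 77% of negative changes are illustrations on simulated data and carry no weight of their own.

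The reach is narrow: the coded version of one conditional sensitivity analysis. The primary MMRM result, the sample size and the blind are unaffected. The missing Hurley Stage term is a secondary slip in the same statement.

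**What to change.** In SAP 7.5.4 and the matching Appendix 2 template:

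- State that Y is the observed AN count at each post-baseline visit, not the change from baseline.
- Replace the distribution and link with `DIST=NEGBIN LINK=LOG`.
- Put baseline AN count (log scale optional), treatment, visit, treatment by visit and baseline Hurley Stage in MODEL.
- Report the Week 16 rate ratio of each imsidolimab dose to placebo with its 90% CI.
- Label the result supportive, because a rate ratio is on a different scale from the difference in mean change in SAP 7.5.1.
- Retitle the template so that it no longer refers to a generalized logit.

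A rank-based or transformed-scale analysis of the change would be equally defensible, provided that it is written out in the same detail. The cost is one template and one SAP sentence. No data collection, sample size or primary analysis changes.
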